13.4. Secondary study parameter(s)

Economically relevant parameters will be gathered within the trial context from individual participants but also the following data from the participant sites/countries will be extracted when possible:

- Patient numbers relative to population and hospital catchment area
- Estimations on the number of emergency department visits associated with acute respiratory infections based on a list of ICD codes.
- For the long-term economic model, the probability of susceptibility to received antibiotics and the resulting illness duration, additional outpatient visits and a second antibiotic course will be estimated based on surveillance data on every site. When needed, assumptions regarding the incidence and hospitalisation rates will be derived from literature and expert opinion

Types of costs: Direct medical costs, direct and indirect non-medical costs.

Hospital costs will be determined using bottom up calculation based on representative sites that have the information available on electronic databases that allow **unit cost prices** assignment to the variables recorded. These descriptive data will include health care utilization for the entire hospitalisation, for ICU stay (unit cost price per hospitalisation day, unit cost price for ICU hospitalisation day). Unit cost price for recorded diagnostic tests and thoracic imaging (referred to the procedure of testing as coded/reimbursed by official nomenclature).

When not available, resource use will be measured as volume of hospital admission days, tests performed, etc).

Analysis of the antibiotic domain based on antibiotic type switches and de-escalation. For the health economic analysis, a decision-tree **deterministic** approach with specification of the base case and alternative scenarios, together with threshold analyses to determine efficient ranges for the values of some parameters. Analysis of the antibiotic domain based on antibiotic type switches and de-escalation.

Regarding qualitative interviews, qualitative data collection and analysis will be done concurrently. Interviews with clinicians and patients, will be analysed using thematic and framework analysis taking an inductive approach. NVivo software will be used to assist with the organisation of data. A thematic framework will be used to chart data across all interviews and will aid comparisons between participants and sites.

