6.2. Secondary endpoints

- Direct costs and indirect costs within 30 days after enrolment.
- Change in quality of life as determined by EQ-5D-5L on day 1, 14 and 30 after enrolment. Extended follow up (up to 6 months) in a subgroup of patients that were initially hospitalised.
- Microbiological results obtained as standard of care and with the diagnostic intervention
- Empirical antibiotics, antibiotic type switches, de-escalation based on antimicrobial agent categories [21]. Prescription of antivirals during the main study.
- Detection of antimicrobial resistance (carriage or infection) related to the diagnostic intervention results compared to standard of care and impact on antimicrobial stewardship guidelines and prevention of hospital acquired infections.
- Decisions regarding isolation measures related to test result.

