10.5. Baseline and follow-up data for health-economic analysis

Follow up Assessments: Timepoints: Day 1, Day 14 and Day 30. · 3 months and 6 months for patients included in Extended Follow up

Individual patient data will be clustered in four main categories:

patient status prior to consultation (including quality of life assessment), diagnostics (including microbiological diagnostic tests and thoracic imaging), medicines (antibiotics and any other prescribed medication at the ER/admission including several parameters, antibiotic prescription in the previous 14 days) and patient follow-up (quality of life, adherence to treatment, duration of complaints).

Quality of life- (see eCRF completion guidelines on guidance) The EQ-5D (<https://euroqol.org>) contains 5-dimensions ("5D") related to everyday living: mobility, self-care, usual activities, pain/discomfort, and anxiety/depression. Patients rate the problems they have with each of these dimensions on a 5-level scale ("5-L") from 1 (no problems) to 5 (extreme problems). The second part of the EQ-5D-5L asks patients to grade their current global health status from 0 (worst health you can imagine) to 100 (best health you can image). The questionnaire form takes ± 5-10 min to administer. It needs to be completed by patient or person who has known the patient for > 5 years. (Order of preference: caregiver > spouse > children 18+ > sibling > other acquaintance). For patient questionnaires, patients will receive a link per email to complete the questionnaires online, which will directly be incorporated into the eCRF and be regarded as source data once digitally completed by the patients. If this is not possible or if patients are seen face to face, questionnaires will be completed per paper (source data) and entered in the eCRF by study staff at the site. In this case paper versions will be stored as source data. The third option to have the questionnaires completed is the use of the Interviewer version in which the study staff will interview the patient and complete the data on the paper form (source data) after which data will be entered in the eCRF.

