13.3. Primary study parameter(s)

Descriptive statistics will be produced and tabular summaries will be presented, stratified according to the allocated group (rapid syndromic testing vs. control). Categorical data will be summarized by the number and percentage of patients in each category. Appropriate summary statistics will be used for continuous variables depending on the distributional assumptions. These include measures of central tendency (mean or median) and dispersion (standard deviation or inter-quartile range).

‘Days on antibiotic treatment’ and ‘Days alive out of the hospital’ will be analysed using a linear regression analysis, including as covariates stratification by age groups and predefined risk factors. Upfront we may expect that the assumption of normally distributed residuals is violated, in which case we will determine the confidence interval by bootstrapping.

Adverse outcome will be analysed using Cox proportional hazards regression adjusted for age groups and predefined risk factors. Risk differences and 90% CI will be inferred by comparing the cumulative incidence of failure at day 30 from the Cox model and bootstrapping for the confidence interval. A 90% CI will be used to be compatible with a one-sided alpha of 0.05.

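### Section 13.4 names only a deterministic decision tree for the health-economic analysis, so the arm difference in 30-day cost would be reported without sampling error

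*Combined protocol and SAP*

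**What the plan says.** Section 6.2 lists "Direct costs and indirect costs within 30 days after enrolment" as a secondary endpoint and, separately, "Change in quality of life as determined by EQ-5D-5L on day 1, 14 and 30 after enrolment".

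Section 13.4 covers the analysis of secondary parameters. On data it says: "Economically relevant parameters will be gathered within the trial context from individual participants". It adds site and country data where these can be obtained. On prices it says: "Hospital costs will be determined using bottom up calculation based on representative sites". Where prices are not available, resource use is to be expressed in volumes such as admission days and tests. On method it names "a decision-tree deterministic approach with specification of the base case and alternative scenarios". The one further element is a search for the values at which the conclusion would change, worded as "together with threshold analyses to determine efficient ranges for the values of some parameters". It gives no interval, bootstrap or probabilistic analysis for costs, and it does not mention EQ-5D-5L.

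Section 10.5 confirms that the economic data set is held at patient level: "Individual patient data will be clustered in four main categories", one of which includes quality of life.

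For the two superiority endpoints, section 13.3 expects non-normal residuals, "in which case we will determine the confidence interval by bootstrapping". Section 13.2 defers a statistical analysis plan until after protocol approval. The combined document contains no separate SAP text.

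**The concern.** The 30-day cost endpoint is a comparison of two randomised arms. Its arm difference is an estimate from a finite sample and has a standard error like any other. A deterministic tree takes point inputs and returns a point result. A scenario shows how the result moves if an assumption changes, and a threshold analysis shows where the conclusion flips. Neither shows how far the result could move if another sample of patients had been randomised.

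At stake is how an apparent saving is read. A point estimate favouring rapid testing could be presented as a finding when the trial's data do not separate it from zero. This matters more here than for a typical secondary endpoint. Section 2 names economic determinants of integrating diagnostics among the aims, section 3 says another work package relies on these trials for cost and quality-of-life variables, and section 10.3 sets up the extension follow-up partly for health-economic purposes.

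**Working it through.** **Plan's own figure.** The documents state no SD, precision or power for cost or EQ-5D-5L, so there is no figure to reproduce on this point.

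**Does any stated method give cost an interval?**
- Section 13.4, scenarios and thresholds: these vary inputs and contain no sampling error.
- Section 13.3, regression and bootstrap: these are written for the primary parameters only.
- Section 13.3, descriptive summaries by arm: these sit under the primary-parameter heading. Even if extended to cost, a within-arm SD or inter-quartile range is not an interval for the difference.

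So none does.

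**Does sampling error exist when unit prices are fixed?** Yes. Cost per patient is the sum over items of (quantity used × unit price). Quantities differ between patients, so the mean cost in each arm varies from sample to sample even if every price is a constant.

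**Illustrative size for cost.** Inputs: 1600 adults in total (section 13.1), hence 1600 / 2 = 800 per arm; coefficient of variation (CV) of 30-day cost assumed at 1.5, range 1 to 2, not from the documents.

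SE of the difference as a share of mean cost = CV × √(2/800) = 0.05 × CV. The 95% half-width = 1.96 × SE.

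| CV (assumed) | SE, % of mean | 95% half-width, % of mean |
|---|---|---|
| 1 | 5.0 | 9.8 |
| 1.5 | 7.5 | 14.7 |
| 2 | 10.0 | 19.6 |

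With 780 per arm, the number required before the drop-out allowance, the multiplier is 1.96 × √(2/780) = 0.099 instead of 0.098, so the range is essentially unchanged.

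**Cross-check with a figure the documents do give.** Hospital days are one of the costed items in section 13.4. Section 13.1 gives an SD of 4 days for days alive out of hospital within 14 days, from a pneumonia population, and tabulates SDs from 3 to 7.
- SD 4: SE = 4 × √(2/800) = 0.20 days; half-width = 1.96 × 0.20 = 0.39 days.
- SD 3: half-width = 1.96 × 0.15 = 0.29 days.
- SD 7: half-width = 1.96 × 0.35 = 0.69 days.

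At SD 4 the half-width is 39% of the 1-day effect that section 13.1 treats as clinically relevant. This is a 14-day proxy, not a 30-day cost, but it shows that sampling error in a main resource item is not negligible.

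**The case against.** The strongest case for the plan has four parts.

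1. **A deterministic model is a legitimate choice for part of this work.** The long-term model draws on site surveillance data and, where needed, published sources and expert judgement. Resampling trial patients cannot represent uncertainty in those inputs, whereas scenarios and thresholds can address it. This stands, and it is why the deterministic analyses should be kept. It does not cover the within-trial 30-day comparison.

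2. **The protocol is an outline.** A SAP is deferred, and section 3 places the economic modelling in another work package. A later document may close the gap. That is possible but cannot be checked here, and section 13.4 does more than stay silent: it names a method for the health-economic analysis, and that method has no sampling error.

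3. **Costs are not observed per patient.** Resource use is, but hospital unit prices come from representative sites only. This stands as a correction to any loose description of the data, and it means that a cost bootstrap first needs a rule for pricing patients at sites without prices. It does not remove sampling error.

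4. **The consequence is limited.** Two likely cost drivers, hospital days and antibiotic days, are analysed with confidence intervals in section 13.3, so readers would see some of the uncertainty. This is true, but those are 14-day outcomes and not the 30-day cost.

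A reader might infer that quality-of-life differences would also be reported without intervals. The documents do not support that. In section 13.4 the deterministic wording describes the health-economic analysis. EQ-5D-5L change is a separate objective and endpoint, and no analysis is specified for it. Silence about a method is not a plan to omit an interval.

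**Conclusion.** The point holds for cost. Section 13.4 names a deterministic tree as the only health-economic method, and if it is followed as written, the arm difference in 30-day cost has no interval. For EQ-5D-5L change the between-arm analysis is simply unspecified.

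The size of the omitted error for cost cannot be computed from the documents. The range of about 10% to 20% of mean cost rests wholly on the assumed CV of 1 to 2 and on complete cost data for 800 patients per arm. It shows the order of magnitude and is not an estimate for this trial.

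Two further readings would go too far: that a deterministic tree is wrong in itself, and that the trial's main conclusions are at risk. The first fails because the tree suits the inputs that come from outside the trial. The second fails because the co-primary tests and the sample size do not depend on the economic analysis. This is a minor weakness that is cheap to repair.

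**What to change.** In section 13.4, or in the deferred SAP, add the following:

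- Report the arm difference in mean 30-day cost with a bootstrap 95% confidence interval, resampling patients within arm and centre. This matches the centre-stratified randomisation in section 10.2 and uses a technique already planned in section 13.3.
- Apply a common set of unit prices to patients at sites that have none, and state the rule in advance.
- Run the decision tree on the same bootstrap draws for its trial-derived inputs.
- Keep the deterministic scenario and threshold analyses for unit prices and for inputs from surveillance, published sources and expert judgement.
- State the between-arm analysis for EQ-5D-5L change, with an interval, to fill the missing detail.

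The cost is some extra analysis work and agreement on the pricing rule. No additional patient data are needed, and the primary analyses and sample size do not change.

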13.5. Mid-term data analysis

A data snapshot will be taken, after the first season, in terms of number of recruited cases per category, impact of seasonal outbreaks or emerging pathogens. Sample size assumptions may also need to be validated.

14. ETHICAL CONSIDERATIONS

14.1. Regulation statement

The study will be performed in accordance with all applicable laws and regulations including the International Conference on Harmonisation (ICH) Guideline for Good Clinical Practice (GCP) the ethical principles that have their origins in the Declaration of Helsinki (current official version: Fortaleza, 2013; <https://www.wma.net/policies-post/wma-declaration-of-helsinki-ethical-principles-for-medical-researchinvolving-human-subjects/>), the updated version of the General Data Protection Regulation (EU) 2016/679 (GDPR), ISO 20916 and other applicable privacy laws.

14.2. Recruitment and consent

The investigator or authorised delegate must obtain written informed consent before any clinical study related procedure/activity takes place. Patients (or, if applicable, their legally accepted representative (LAR) will be approached for the study by the investigator or authorised delegate. Written versions of the Participant Information Sheet and Informed Consent will detail the exact nature of the study; the implications and constraints of the protocol; and any risks involved in taking part. It will be stated clearly in the patient information letter that participation in this study is completely voluntary and that withdrawal is possible at any time and without any consequences. Staff will explain the details of the study to the participant and/or legal representative (if applicable) and allow them time to discuss and ask questions. The consenting party will be asked to sign and date an informed consent form. Obtaining a patient's consent to participate in medical research may be complicated by COVID-19 measures. In the case of the patient being in isolation and unable to sign, he/she will give his/her oral consent, the researcher will sign directly, and the patient will sign as soon as possible after completion of the isolation period. Deviations in consent procedures might occur per participating country, following national law and locally accepted procedures with regards to challenging COVID-measures.

Participant Information Sheets will be available in the common local language. Written Informed Consent will be confirmed by the dated signatures of the participant and by the person who presented and obtained the informed consent. The person obtaining consent must be suitably qualified and experienced and be authorised to do so by the Principal Investigator. A copy of the signed Informed Consent will be given to the participants. The original signed form will be retained at the study site.

If a patient is illiterate, an impartial witness must be present during the entire informed consent discussion. All items addressed in the Patient Informed Consent Form must be explained. The language used shall be as non-technical as possible and must be understandable to the patient in the impartial witness, where applicable.

For clinicians taking part in interviews we will provide the Clinician Participant Information Sheet, the Clinician Interview Informed Consent Form, the Clinician Interview Invitation and the Clinician Interview Topic Guide.

14.3. Withdrawal of individual patients

Patients are free to withdraw consent at any time without providing a reason. Patients who wish to withdraw consent for the study will have anonymized data collected up to the point of that withdrawal of consent included in the analyses. The patient will not contribute further data to the study. Data up to the time of withdrawal will be included in the analyses unless the patient appeals to the 'right to be forgotten' according to the national GDPR regulations. The investigator can decide to withdraw a patient from the study for urgent medical reasons. Enrolled patients meeting one or more of the exclusion criteria *prior* to randomisation, will be withdrawn by the investigator. Patients withdrawn prior to randomisation will be replaced (i.e. they will not count towards the sample size). Patients withdrawn after randomisation will not be replaced.

The participants cannot be enrolled at the same time into any interventional clinical study unless it is a COVID-19 study that does not interfere with this study. Patients may be co-enrolled in another observational study if the local study coordinators have been informed and have given their approval, to ensure the other study would not interfere with the results of this study or compromise patient welfare.

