 - For initially non-admitted patients: any admission or death within 30 days
 - For initially hospitalised patients: i) any readmission, ii) ICU admission ≥ 24 hours after hospitalisation, or iii) death within 30 days

Nature and extent of the burden and risks associated with participation, benefit and group relatedness: Participation in the study involves collection of data that can be obtained from medical charts and follow up questionnaires and interviews. Respiratory samples (e.g. nasopharyngeal swab, sputum) will be obtained as standard of care and diagnostic intervention (Biofire FilmArray) will be used only for participants randomised to the intervention. Based on the results of diagnostic testing (BioFire FilmArray) antibiotics may be withheld when deemed unnecessary, or a different antibiotic class may be selected when certain bacterial pathogens are detected. The risks and benefits of management decisions, complemented with adequate training, are subject to the current investigation.

3. GENERAL CONSIDERATIONS WORK PACKAGE 4 AND VALUE-Dx OVERVIEW

The purpose of VALUE-Dx consortium (www.value-dx.eu) is to facilitate and accelerate the rigorous assessment and implementation of (new) diagnostic technologies into healthcare settings, by establishing the infrastructure, methods, processes and approaches needed to understand, evaluate, assess, and demonstrate the multi-faceted value of diagnostics and overcome the associated barriers to their widespread adoption and use. VALUE-Dx focuses its research on **community acquired acute respiratory tract infections (CA-ARTI)**.

The objectives of VALUE-Dx are:

- To design a health-economic framework to assess and demonstrate the value of diagnostics both for individual patients and for public health impact by reducing antibiotic use and subsequent antibiotic resistance among patients;
- To establish a sustainable European Standardised Care Network adequately trained and resourced to conduct clinical trials evaluating the value of diagnostics;
- To design and implement clinical studies to demonstrate the value of diagnostics in the optimal management of CA-ARTIs;
- To explore, define and attempt to resolve the psychological, ethical and social barriers which prevent the more widespread adoption of diagnostics delivering healthcare to the population.

The clinical studies, to be implemented in WP4, aim to gather evidence on:

- i) doses or days of antibiotics prescribed,

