6. STUDY PARAMETERS/ENDPOINTS

6.1. Main study parameter/endpoint

Co-primary study endpoints:

1. Days alive out of hospital (superiority endpoint), within 14 days after study enrolment
2. Days on Therapy (DOT) with antibiotics (superiority endpoint), within 14 days after study enrolment
3. Adverse outcome (non-inferiority safety endpoint)
 - For initially non-admitted patients: any admission or death within 30 days after study enrolment
 - For initially hospitalised patients: i) any readmission, ii) ICU admission \geq 24 hours after hospitalisation, or iii) death within 30 days after study enrolment

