10.3. Data collection

A secured electronic case record form (eCRF) will be specifically designed for this study for data capture.

- **Main study** (Follow up until 30 days) – Standard of care clinical and microbiological data will be collected but not study specific biological samples will be obtained for research purposes. The **clinical data set** will summarize the illness episode and outcome, microbiological testing and antimicrobial use including the total hospitalisation or, in case of discharge, the time window defined on the primary endpoints. Information including data for health economic analysis will be collected on day of enrolment, day 14 (visit window: day 14 – 16) and on day 30 (visit window: day 30 – 32), after randomisation. Participants/LAR will be asked to consent to being contacted by study staff for the follow-up visits to minimise loss to follow-up. In case of failure to successfully contact participant/LAR at the end of trial participation, the participant's general practitioner/family doctor will be contacted to complete information on the primary endpoints.
- **Extension study** – in a subset of patients (around 300 patients per arm), patients that were initially hospitalised will be followed post-discharge at month 3 (visit window: +7 days) and month 6 (visit window: +7 days) to study health economic and social impact.
- Qualitative Evaluation: Only clinician (semi-structured) qualitative interviews

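### Section 14.3 offers only one form of consent withdrawal, which ends all data collection, so co-primary endpoint data that records could still supply are lost

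*Combined protocol and SAP*

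**What the plan says.** Section 14.3 lets patients withdraw consent at any time. From then on, "The patient will not contribute further data to the study". There is no exception for chart data or vital status, and no lesser level of withdrawal is described. On data already collected, the same section says "Data up to the time of withdrawal will be included in the analyses", subject to the patient's right to have them erased. It adds: "Patients withdrawn after randomisation will not be replaced".

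The endpoints do not depend mainly on talking to the patient. The Summary (section 2) says: "Participation in the study involves collection of data that can be obtained from medical charts and follow up questionnaires and interviews". Section 10.3 provides for failed contact at the end of participation: "the participant's general practitioner/family doctor will be contacted to complete information on the primary endpoints". Section 10.2 says that follow-up is completed when the allocated test is not carried out. Neither of these provisions covers withdrawal of consent.

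The first co-primary endpoint in section 6.1 is "Days alive out of hospital (superiority endpoint), within 14 days after study enrolment". Antibiotic days are counted over the same window, and the adverse outcome runs to day 30. Under section 13.3 each 14-day count "will be analysed using a linear regression analysis", and the adverse outcome goes into a Cox model. Section 13.3 gives no rule for an incomplete 14-day window. Section 13.2 defers the statistical analysis plan to a later date.

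**The concern.** Patients who withdraw often object to one thing, such as further calls or questionnaires, and not to a look at their hospital record. If the protocol offers only full withdrawal, site staff have no described way to keep the part the patient would still allow. The data lost are the co-primary endpoints themselves, and no later analysis rule can recover what was never collected.

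The trial is open-label and patients can know whether they had the rapid test, so withdrawal could differ by arm in rate or timing. Success needs superiority on at least one 14-day count and also non-inferiority on the adverse outcome, so loss on any of the three matters. The two counts are the more exposed. A Cox model can censor at withdrawal (though informative withdrawal could still bias it), whereas a linear regression on a 14-day total needs a value for the whole window.

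**Working it through.** **1. Routes to the endpoints, side by side.**
- Patient cannot be reached: general practitioner contacted (10.3).
- Allocated test not carried out: follow-up completed (10.2).
- Consent withdrawn: nothing after that date (14.3).
- Patient wants no contact but accepts record follow-up: not described.

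**2. Room for loss.** Inputs from section 13.1: margin 5%, incidence 10% in both arms, one-sided alpha 0.05, power 0.95.
- Non-inferiority n per arm = 2 × 0.10 × 0.90 × (1.645 + 1.645)² / 0.05², which gives 780 and matches the plan.
- Superiority n per arm, with SD 4, effect 1 day, two-sided alpha 0.025, power 0.90 and factor 1.15: 2 × 4² × (2.241 + 1.282)² × 1.15 = 457, which also matches.
- Allowance: 1600 − 2 × 780 = 40, and 40/1600 = 2.5%. The plan states no drop-out rate; this is what its figures imply.
- Non-inferiority power = Φ(0.05/√(2 × 0.10 × 0.90/n) − 1.645): 95.4% at 800 per arm, 95.0% at 780, 94.6% at 760 (5% lost), 93.5% at 720 (10% lost). The power cost is small.

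**3. Illustration of bias in days alive out of hospital.** None of these assumptions is in the documents: a mean of 10 days spread evenly over the 14, withdrawal on day 3 or day 7, a 3-point difference in withdrawal between arms, and partial counts entered as if they were 14-day totals.
- Days lost per withdrawer = 10 × (14 − d)/14: 7.86 at d = 3 and 5.0 at d = 7.
- Shift in the arm difference: 0.03 × 7.86 = 0.24 day; 0.03 × 5.0 = 0.15 day.
- Benchmarks: relevant effect 1 day; standard error 4 × √(2/800) = 0.20 day.
- A 3-point difference fits inside the allowance: 4% against 1% of 800 is 32 + 8 = 40 patients.

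Over a wider range, with 4 to 12 counted days lost per withdrawer, the shift is the difference in withdrawal times the days lost:
- 1 point: 0.04 to 0.12 day.
- 2.5 points: 0.10 to 0.30 day.
- 5 points: 0.20 to 0.60 day.
- 10 points: 0.40 to 1.20 days.

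For antibiotic days only the remaining treatment days are lost, so the shift would usually be smaller.

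**4. Equal withdrawal w in both arms, same assumption about partial counts.** There is essentially no false difference, only a diluted effect (1 − w) and a larger SD, √(16 + w(1 − w)L²), with L the days lost. At 800/1.15 per arm and L from 7 to 12, superiority power falls from 99.2% to:
- 97.0–98.4% at 2.5% withdrawal.
- 92.9–97.1% at 5%.
- 81.0–93.0% at 10%.

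**The case against.** Stopping collection when a patient fully withdraws consent is correct, and nothing here disputes it. Beyond that, the case for the plan has four parts.

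- A reader might infer that anyone who only wants no more calls must leave the study altogether. The documents do not say so. The rule in 14.3 covers patients who withdraw consent for the study, while 10.3 treats contact for follow-up visits as something participants are separately asked to agree to. The consent form is not available for this review and may already offer levels. This stands, and limits the point to what the protocol text leaves out.
- A reader might also infer that 14-day totals will be cut short, because pre-withdrawal data are analysed and the counts go into a linear regression. The documents never say that a partial count stands as a total. The sentence in 14.3 can be read as permission to keep data already collected, and exclusion or imputation would also fit the text. This stands.
- A further tempting reading is that the two superiority endpoints would be biased in opposite directions. If only observed days are summed, both counts fall, and only their favourability differs. If days alive out of hospital is instead 14 minus recorded hospital or dead days, unobserved days count as good days and both endpoints move the favourable way. The protocol does not state the derivation, so no direction is established.
- A rule for incomplete windows belongs in the deferred statistical analysis plan. That is fair for the analysis rule. It does not answer the collection gap, because an analysis plan cannot restore data nobody was permitted to collect.

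**Conclusion.** The point holds as a gap in 14.3: no stated option keeps record-based follow-up for a patient who wants contact to end, although the protocol already obtains the same endpoints without patient contact in other situations. The consequence is avoidable loss of co-primary data against an implied allowance of 2.5%.

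The size of any bias cannot be derived from the documents. The 0.15 to 0.24 day shift depends on the assumed rate difference, timing and mean, and on partial counts being used as totals. It is about the size of one standard error (0.20) and well below the 1-day effect. Differential withdrawal is plausible in an open-label trial but undocumented. With equal withdrawal at or below 5%, power for days alive out of hospital stays above the planned 90% in every case shown. This is therefore a worthwhile, inexpensive improvement and not a flaw that threatens the trial's conclusions.

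**What to change.** In 14.3, and in the consent form if it does not already do so, offer two levels of withdrawal:

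- (a) no further contacts or questionnaires, with the day-14 and day-30 co-primary endpoints still taken from hospital records or the general practitioner, with the patient's agreement;
- (b) full withdrawal, with no further collection, whenever the patient asks for it.

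Record the level and date in the eCRF, and report both by arm.

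As a minor accompanying point, the statistical analysis plan should treat days after full withdrawal as missing: not as zero, and not as part of a completed 14-day total. Multiple imputation of the remaining days is one suitable method.

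The cost is an amendment to the protocol (and possibly the consent form), an eCRF entry for level and date, and one extra question to the patient at withdrawal.
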